Aim 2. To assess the feasibility and acceptability of the optimized *MeSSSSage* intervention. In Phase 2 we will evaluate the feasibility and acceptability of two intervention components using a controlled 4-arm factorial design (n=160; 40 per arm): 1) real-time mobile voice information and support group alone, 2) asynchronous/on-demand text-based group support only, and 3) real-time mobile voice information and support group plus asynchronous/on-demand text-based group support. Feasibility and acceptability will be assessed via back-end data, surveys, and IDIs with purposively selected participants (n=30) and moderators.

Aim 3. To explore the preliminary effectiveness of the optimized *MeSSSSage* intervention components on six-month maternal and neonatal health outcomes. Phase 2 data will help us develop a preliminary understanding of the impacts of the intervention components on MCH health-related knowledge, behaviors and outcomes including exclusive breastfeeding, immunization, family planning uptake, postnatal visits, mental health and empowerment; however, it is not statistically powered to formally assess effectiveness.

This study is significant and innovative in addressing key priorities of NICHD's Pregnancy and Perinatology Branch and using systematic, user-centered and experience-driven design approach. These results will inform the most acceptable, feasible, and potentially efficacious intervention design to be robustly tested through an R01 mechanism to assess effectiveness for maternal and infant health outcomes, explore other research questions relevant to intervention development and scale-up for postnatal health among South Asian women, and explore generalizability across populations.

Significance

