Women are eligible if they are over the age of 18 and this is their first birth. Women with high risk pregnancies will be ineligible for participation, and women will be removed from the study if they deliver preterm, suffer severe maternal complications (c-section or hospitalization), or they or their baby are otherwise sick in the first week postnatal. When the women deliver their infants, the ASHA and facilitator will inform the research team, and women will be assigned to groups based on date of delivery, since women in each group ideally will have all delivered their babies within approximately two weeks of each other.

Back-end data will be captured from all participants. After two months (eight group meetings) we will conduct a brief phone survey with all participants and in-depth interviews with a subset of approximately half of the participants, purposively selected to obtain a range of frequency and intensity of participation.

Surveys and backend data: All 48 respondents will be called via phone to participate in a short (10 min) survey about their experiences with *MeSSSSage* group components, including preferences regarding functions and modalities and level of satisfaction with each, using likert-type response scales (1-5). Data will be recorded on a tablet confidentially. We will calculate means and standard deviations for each of the preferences and function variables. Additionally, each group discussion will be audio recorded, transcribed, and translated into English. We will analyze the content of the group discussions for function, using *Atlas.ti* software. We will also review level of intervention engagement including text-messaging (number and topic), the number of participants per session, number of participants who engage with the health worker and each other, etc. The study team has analyzed the data collected in previous technological studies, and we will use a similar method. Data will be analyzed using STATA version 15 (College Station, Tx).

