Procedures: Unless found not feasible or acceptable within Phase 1 activities, women will be recruited using the approach described above (Aim 1). At the time of enrollment, the study protocol will be described to the women following informed consent procedures and written informed consent will be obtained from interested women, and their phone numbers will be collected (and tested). Women who do not have a phone will be provided with a phone and all participants' airtime will be covered for the length of the six-month research project. If they consent to participate, women will be randomly enrolled into one of the three study arms, or control, using a random number generator. We will test each study condition using two groups of women, with intervention initiation staggered one month apart. Women in the control group will receive the standard of care for women in this population. All women will be given 50 Indian Rupees for participation in each session (in addition to airtime and phone if needed), and ASHAs will receive 150 Indian Rupees for moderating each session. Assessment of feasibility and acceptability (Aim 2) and preliminary effectiveness (Aim 3) will be accomplished using a mixed-methods approach that will include quantitative surveys, in-depth interviews, and technology assessment.

Survey data collection: At study enrollment, a baseline survey will be administered by a research assistant in the respondent's home. Roughly six months postnatal, after having the opportunity to participate in approximately 24 MeSSSSage sessions (final number to be determined in Phase 1 activities), women will be visited in their homes for the endline survey. We will also capture women's health record cards and ASHA registers to validate self-reported health outcome data. Data will be collected on a tablet using REDCap mobile research administration software (a highly secure platform), stored in a password protected database at UCSF, and no identifiable information will be included with the data (names, phone numbers, and addresses will be stored separately and linked by an ID).

In-depth interviews: Additionally, in-depth interviews (IDIs) will be conducted with a selection of 10 women from each intervention condition (30 IDIs), purposively sampled based on high/low participation rates determined by the end line survey. We will collect data on experiences with MeSSSSage and how to improve it.

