Technology assessment: Finally, we will collect and analyze the quantitative backend data from the prototype to gain more insight into women's participation in the intervention, including attendance and level of participation in group interactive educational sessions, use of mobile social support platform (number of posts, frequency, topic), etc. Text data from transcripts of the educational sessions and content of group messaging will be analyzed for content in order to understand primary educational needs and interests for postnatal women.

Group moderator survey and interview: ASHA facilitators moderating the groups will be asked to respond to a short questionnaire after each group session to understand: preparation and delivery time, content, efficiency, acceptability and satisfaction with the group model, perspectives of impact, challenges, and any follow-up/referral necessary.⁴⁰ Regarding facilitation of groups that receive the text-based messaging intervention component only, ASHA facilitators will report on experiences in the prior week. We will also conduct monthly semi-structured interviews with each of the ASHA facilitators to understand their own preferences around the group components, their experiences preparing for and conducting the sessions, and their perspectives on mobile provision of education, care, and support.

Measures: The baseline survey content will include sociodemographic characteristics and knowledge about maternal and infant health, self-efficacy, and perceived social norms regarding MCH-related health promoting behaviors. The endline survey will include acceptability questions such as women's satisfaction with and perceptions of MeSSSSage, maternal and infant knowledge-, behavior-, and health-related questions including about breastfeeding, complementary food introduction, immunization, family planning uptake, maternal physical and mental health, etc. which have previously been used in this setting (Table 3)⁴.

Table 3: Participant survey measures (Phase 2)

Category	Measures
Sociodemographic characteristics	Age, age at marriage, educational attainment, caste, language spoken, household assets, women's status/decision-making, social support and relationship quality.
Health-related knowledge (effectiveness)	Knowledge on maternal and neonatal danger signs, best practices for infant care, family planning.

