Health-related behaviors (effectiveness)	Breastfeeding and complementary food introduction practices (breastfeeding initiation, length of exclusive breastfeeding, length of breastfeeding, timing of complementary food introduction), appropriate management of early childhood illnesses.
Health outcomes (effectiveness)	Early childhood immunization, postnatal depression and anxiety, postnatal family planning adoption.
Intervention perspectives (feasibility, acceptability)	Self-reported engagement in intervention components and topics, satisfaction with intervention components, likelihood of participating again, likelihood of recommending program, value on knowledge and social support gained from participation.

Analysis

Aim 2. Feasibility and acceptability of the optimized MeSSSSage intervention components. We will use a mixed methods approach, triangulating data from quantitative baseline and endline data, qualitative IDIs, and technology assessment. Feasibility and acceptability will be measured by participation rates at each session, trajectories of participation over time, and user engagement (via technology assessment backend data). Women's reports of use and satisfaction in the survey and the qualitative data will shed light on barriers and facilitators to participation. Moderator acceptability will be assessed by satisfaction, fidelity to topic/content based on protocol and perspectives on impact. We will test for differences in feasibility and acceptability between the three intervention arms to understand if both components (group meetings and text) or only one is the best approach, using ANOVA for continuous outcomes and chi-square or Fisher's exact tests, as appropriate, for categorical outcomes.

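### Phase 2 interviewees are classed as high or low participators from endline self-report although back-end logs exist, which leaves women without an endline survey outside the frame

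*Protocol*

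**What the plan says.** The Protocol's Phase 2 paragraph on in-depth interviews plans "a selection of 10 women from each intervention condition (30 IDIs" in total), with the women "purposively sampled based on high/low participation rates determined by the end line survey". The endline survey is a home visit at roughly six months, after the chance to attend about 24 sessions; the visit does not depend on attendance. In Table 3, the one entry on participation is "Self-reported engagement in intervention components and topics".

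The protocol has a second source. The Technology assessment paragraph collects back-end data, "including attendance and level of participation in group interactive educational sessions, use of mobile social support platform (number of posts, frequency, topic"). The Aim 2 analysis measures feasibility and acceptability by "participation rates at each session, trajectories of participation over time, and user engagement (via technology assessment backend data"). It then looks to the women's survey reports and the qualitative data to explain what helps or hinders participation.

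No cut-off between high and low is given, and nothing is said about interviewing a woman who has no endline survey. The SAP covers Phase 1 only and is silent on this.

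**The concern.** The interviews are meant to explain why some women took part and others did not, so the variable used to choose the women matters. The plan takes that variable from a self-report over about six months, while the participation that the interviews should explain is logged. Two weaknesses follow.

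- **Frame.** A woman with no endline survey has no participation value under the rule and cannot be chosen. Her survey report is missing too, so both sources that Aim 2 names for barriers lose her.
- **Label.** A woman whom the logs show as a low participator may be interviewed as a high one. The record cards and ASHA registers do not catch this, because they are collected to validate health outcomes, not participation.

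At stake is the quality of the qualitative account of participation and how well it can be set against the logs.

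**Working it through.** **1. The plan's own figures.** The Specific Aims give a "controlled 4-arm factorial design (n=160; 40 per arm"), and the interview paragraph gives 10 women per intervention arm.

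- Interviews: 10 × 3 = 30, as stated.
- Women: 40 × 4 = 160, as stated; in the three intervention arms, 40 × 3 = 120.

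**2. Women outside the frame.** Let d be the share with no endline survey. The documents give no value, so d is an assumption. Excluded per arm = 40 × d; excluded overall = 120 × d.

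| d (assumed) | Excluded per arm | Excluded of 120 | Classifiable per arm |
|---|---|---|---|
| 0% | 0 | 0 | 40 |
| 5% | 2 | 6 | 38 |
| 10% | 4 | 12 | 36 |
| 20% | 8 | 24 | 32 |

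Even at 20%, 32 women per arm remain from whom to choose 10. The number of interviews is not threatened; the range of women who can be heard is.

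**3. Stopping sessions is not the same as missing endline.** Let s be the share of an arm that stops attending and c the endline completion among them. Stoppers who can still be selected = 40 × s × c. With s = 20% (assumed), 8 women stop. At c = 100%, 75%, 50% and 0%, the number still selectable is 8, 6, 4 and 0. Only the remainder is lost.

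**4. Label error under a fixed cut.** Let L be the true share of low participators, f the chance that a low participator reports high, and g the chance that a high participator reports low. All three are assumptions.

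- Wrong among those labelled high = L·f / [L·f + (1 − L)(1 − g)]
- Wrong among those labelled low = (1 − L)·g / [L(1 − f) + (1 − L)·g]

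Over-reporting only (L = 0.5, g = 0):

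- f = 0.2: high group 0.10 / 0.60 = 17% wrong; low group 0%.
- f = 0.4: high group 0.20 / 0.70 = 29% wrong; low group 0%.

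With under-reporting added (g = 0.05 to 0.10, f = 0 to 0.4), the error in the low group runs:

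- L = 0.5: from 0.025 / 0.525 = 5% to 0.05 / 0.35 = 14%.
- L = 0.3: from 0.035 / 0.335 = 10% to 0.07 / 0.25 = 28%.

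So one-way over-reporting contaminates the high group and shrinks the low group. The low label itself fails only with under-reporting, or with a relative cut such as a median split.

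**5. The two sources side by side.** Endline self-report exists only for women surveyed and relies on recall. The back-end record covers all 40 women in each intervention arm whether or not they answer endline. The plan uses it to measure engagement but does not name it for interview selection.

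**The case against.** A reader might infer more than the documents support.

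- *That women who dropped out cannot be interviewed.* Not so. Endline is a home visit that does not depend on attendance, so a woman who stops after two sessions and is visited stays in the frame. Only those without an endline survey are excluded.
- *That the low group is mislabelled.* The documents contain no measure of reporting error. It is a risk, and over-reporting under a fixed cut would spoil the high group instead.
- *That Aim 2 will understate barriers.* This does not follow. The back-end feasibility measures do not depend on who is interviewed. ASHAs follow up women who fall away, to learn why, and moderators report challenges after each session and are interviewed monthly. Of this, the ASHA follow-up is not described as recorded or analysed, and none of it feeds interview selection, so these are partial substitutes.
- *That Phase 2 departs from Phase 1.* In Phase 1 the interviewees are "purposively selected to obtain a range of frequency and intensity of participation", but no data source is named, so there is no inconsistency to point to.

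The strongest case on the other side is one of proportion. This is purposive sampling in an unpowered pilot, the protocol expects no retention problem, and Phase 2 is still to be finalised after Phase 1. The wording might also have meant participation as it stood by the time of endline. That limits the importance, and I accept it. But the sentence names the survey as the source. It is a stated rule, not a detail left open, and if the logs were intended it needs correcting anyway.

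**Conclusion.** The point holds in a limited form. The rule relies on a self-reported measure, available only for women surveyed at endline, when the trial already plans to hold a logged one. For an assumed endline loss of 0 to 20%, it shuts out 0 to 8 women per arm (0 to 24 of 120). It is plausible, but not documented, that they include low participators. Misclassification is possible, mainly of over-reporters into the high group if over-reporting dominates; its size rests wholly on assumed error rates. The consequence is confined to Aim 2's qualitative explanation of participation. The back-end feasibility measures are untouched. It is worth changing, and of modest importance.

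**What to change.** Amend the sentence in the Phase 2 interview paragraph along these lines: *Within each intervention arm, high and low participation will be defined from the back-end data, with a cut-off fixed before selection: attendance for the voice component, number and frequency of posts for the text component, and both in the combined arm. Women who stopped participating or missed the endline survey may be invited. Ten women per arm will be interviewed.* Keep the endline self-report only as a comparison with the logs. The protocol should also say how the two components are combined in the third arm.

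**Cost.** About one sentence to change; the data are already planned and the number of interviews stays at 30. The protocol schedules tool development and ethics modifications between the phases, so there is a natural point to do it.

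**Downside.** Some women who missed endline may be untraceable or may decline; the change stops the rule from excluding them but does not find them. Post counts also miss women who read without posting, so low posting in the text arm should not be taken as proof of low engagement.

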The current national guidelines for postnatal care in India are for women to receive three home visits from an ASHA within the first week following childbirth.^{4,9} In this setting, women are seen by an Accredited Social Health Activists (ASHA) in pregnancy and postpartum. The role of the ASHA in postnatal care is to counsel the mother on recognition of and referral for complications. The ASHA also counsels the mother on adoption of postpartum family planning. For newborns, the ASHA provides skin, eye and cord care, monitors infant weight gain, supports exclusive breastfeeding, and provides general newborn care and referral. **However, data from our study state, Haryana, suggest that less than half of women receive any postnatal care,**⁴ and ASHA visits are typically short, all of which restricts the information and support that women receive in the postnatal period.

Phase 1: Aim 1. To develop optimal intervention functions and mHealth technology delivery platforms for education and peer support among postnatal women in rural India: The prototype MeSSSSage will include a weekly mobile call-in group meeting, including recently delivered women and moderated by one trained health worker, an experienced ASHA facilitator. Each group will consist of 12 women whose infants were born within approximately two weeks of each other. Women will attend these group meetings by calling in on their mobile phone, and the meetings will last approximately one hour. In each group, the ASHA facilitator will provide approximately 20 minutes of health education specifically tailored to the common health needs of the mother and infant at the specific infant age, followed by 40 minutes for group discussion. Aim 1 will inform exact length of education and discussion per meeting), and if and at what frequency reminder messages are required.

Development of optimal modalities: We will pilot the prototype MeSSSSage platform in three groups of recently delivered women for a period of two months by testing different modalities over that time, as described in **Table 1** (N=48). The goal of this formative phase is to orient women to a variety of experiences to reflect on when seeking their feedback, so as to design the most appropriate intervention for full piloting.

Table 1: Modalities to be explored to identify optimal intervention functions, processes and platforms (Phase 1).

Modality	Description of modalities	Goal

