Phase 2: Pilot test of optimized intervention, assessment of feasibility and acceptability (Aim 2) and preliminary effectiveness on maternal and infant health outcomes (Aim 3). After analysis of Phase 1 data, *MeSSSSage* will be adapted based on participant feedback and content will be expanded to cover topics relevant to the first six months of the postnatal period. If data from Phase 1 suggest that the tested mobile group forum modalities are not appropriate for this population, we will adapt our study protocol to explore other feasible means of providing information and support (e.g., SMS or video). We anticipate developing and testing two different modalities of postnatal education and support in a factorial design with an additional control arm for a total of four different group compositions. All women, including the control group, will receive the standard of care provided by the Government of India and described above. We will conduct a pilot test of the intervention using two groups per intervention modality for a total of eight separate groups, a total of 160 women (Table 2). Exact group structure and duration will be informed by Aim 1, but we anticipate the following:

Table 2: MeSSSSage components to be tested in feasibility and acceptability assessment (Phase 2).

	Arm 1	Arm 2	Arm 3	Control
Real-time live voice call group meeting: Interactive educational program with scripted didactic component plus discussion/question. Lead and moderated by health professional.	X		X	
Text-based, asynchronous, on-demand social support: App-based small group text-based communication. Moderated by health professional.		X	X	
Standard of care: 3 visits in the first 7 days postnatal (facility and home)	X	X	X	X

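### The Aim 2 tests between intervention arms make no allowance for the two groups in which each arm is delivered, so p-values are too small if outcomes correlate within groups

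*Protocol*

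**What the plan says.** Allocation is by woman (Protocol, Phase 2, Procedures): "women will be randomly enrolled into one of the three study arms, or control, using a random number generator". Delivery is by group. The same section says: "We will test each study condition using two groups of women, with intervention initiation staggered one month apart". The opening of the Phase 2 section says: "We will conduct a pilot test of the intervention using two groups per intervention modality for a total of eight separate groups", with 160 women in all. That structure is provisional: "Exact group structure and duration will be informed by Aim 1, but we anticipate the following".

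Under Analysis, Aim 2, feasibility and acceptability are measured by "participation rates at each session, trajectories of participation over time, and user engagement", alongside survey and interview data. The protocol then says "We will test for differences in feasibility and acceptability between the three intervention arms", in order to judge whether both components or only one should go forward, "using ANOVA for continuous outcomes and chi-square" or Fisher's exact tests for categorical ones. No group term, group-level summary, ICC or design effect appears in either document.

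The Sample Size section says that the study is not formally powered and that the sample is adequate to describe feasibility and acceptability. The SAP likewise says that both phases were sized for feasibility. Its own analysis text covers Phase 1 only.

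**The concern.** One-way ANOVA, chi-square and Fisher's exact test, applied to women, take the 40 women in an arm as 40 independent observations. Several features of the design make correlation within a group plausible:

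- Live voice sessions are held by group (Arms 1 and 3), and the text component is small-group communication (Arms 2 and 3).
- Attendance is measured session by session.
- The Sample Size section gives interaction among the women as a reason for the group size.
- The Phase 1 prototype group is "moderated by one trained health worker, an experienced ASHA facilitator". The protocol does not say how moderators are assigned to groups in Phase 2.

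With two groups per arm, one unusual group is half of the arm. A small p-value produced by that group could be read as evidence for or against a component, and the section on expected outcomes says that the pilot informs the design of a larger trial.

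**Working it through.** **Inputs from the protocol.** 4 arms x 2 groups x 20 women = 160, which reproduces the stated total and the 40 per arm. The Aim 2 comparison uses 3 intervention arms: 6 groups, 120 women.

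**Assumptions.** The documents give no alpha, ICC, outcome rates or dropout for this comparison. I take a nominal 5% level, equal groups, no dropout, ICC from 0 to 0.10, and true rates of 0.5, 0.7 and 0.9 for binary outcomes.

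**Analytic size of the ANOVA, nothing shared across arms.** With total variance 1, the ratio of expected mean squares when there is no arm effect is

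(1 - ICC + 20 x ICC) / (1 - ICC + (60/117) x ICC).

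The critical value of F(2,117) is 3.074.

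- ICC 0.01: 1.19/0.995 = 1.196; P(F > 3.074/1.196) = 0.081
- ICC 0.05: 1.95/0.976 = 1.999; P(F > 3.074/1.999) = 0.219
- ICC 0.10: 2.90/0.951 = 3.049; P(F > 3.074/3.049) = 0.368

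The design effect, 1 + 19 x ICC, is 1.19, 1.95 and 2.90. The 40 women per arm are then worth 40/1.19 = 33.6, 40/1.95 = 20.5 and 40/2.90 = 13.8.

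**Simulated ANOVA rejection rate with no true difference** (100,000 trials per setting). Columns give the share of the group variance that is common to all arms, for example through start date.

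| ICC | None shared | Half shared | All shared |
|---|---|---|---|
| 0 | 0.051 | 0.050 | 0.051 |
| 0.01 | 0.081 | 0.064 | 0.050 |
| 0.02 | 0.114 | 0.081 | 0.049 |
| 0.05 | 0.218 | 0.132 | 0.046 |
| 0.10 | 0.370 | 0.221 | 0.044 |

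If the ICC differs by arm, with nothing shared, the rate is 0.182 for (0.01, 0.01, 0.10) and 0.280 for (0.10, 0.10, 0.01).

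**Binary outcomes, nothing shared** (beta-binomial, 400,000 trials; ranges run over the three true rates).

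| ICC | Chi-square, 3 arms | Fisher, 3 arms | Fisher, one pair of arms |
|---|---|---|---|
| 0.01 | 0.072-0.088 | 0.067-0.075 | 0.028-0.050 |
| 0.05 | 0.196-0.232 | 0.186-0.211 | 0.083-0.129 |
| 0.10 | 0.331-0.382 | 0.318-0.361 | 0.149-0.218 |

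Pairwise Fisher is conservative to begin with (0.017-0.033 at ICC 0), so it stays at or below about 5% at ICC 0.01.

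**Other group structures, ANOVA, nothing shared.** Four groups of 10 per arm give 0.064, 0.128 and 0.211 at ICC 0.01, 0.05 and 0.10. Two groups of 12, the Phase 1 group size, give 0.067, 0.148 and 0.251.

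**Analysis of group means.** With 6 groups and 3 arms, 6 - 3 = 3 error df remain (critical F 9.55); blocking on start date leaves 2 (critical F 19.0). With equal ICCs and nothing shared, the 3 df test rejects 0.050-0.052. With unequal ICCs it rejects 0.053-0.060, and it falls to 0.019 when everything is shared at ICC 0.10. The blocked test rejects 0.049-0.054 throughout. For group proportions the rates are 0.047-0.055 (3 df) and 0.043-0.052 (2 df).

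**The case against.** The strongest reply is that this is provisional text. Both documents are titled Phase 1, the Phase 2 structure is only anticipated, and the protocol schedules tool development and IRB modifications before Phase 2. A one-sentence list of tests is not a final analysis plan. The study claims no power, sets no alpha or decision rule, and weighs the tests alongside interviews, surveys and backend data. The unit of analysis is not spelled out either: participation at each session could be summarised in other ways. The ICC is unknown, and because groups start a month apart, part of any group difference may be calendar-related and common to the arms. With 80% of the group variance shared, ANOVA rejects only 5.5%, 7.9% and 11.1% at ICC 0.01, 0.05 and 0.10. For chi-square, sharing half brings the rates to about 6-7%, 11-14% and 17-23%.

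Most of this bears on size and severity, and it stands there. It does not remove the point. Lack of power concerns missed effects, whereas the problem here is false positives. A woman-level analysis is the natural reading of the named tests, especially for survey items. They hold their level only if group correlation is absent or almost wholly shared across arms, and the plan argues for neither. Because Phase 2 comes later, the wording can be corrected before its data exist.

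**Conclusion.** The concern holds, conditionally. The tests named for Aim 2 ignore the groups in which the intervention is delivered, and ANOVA and chi-square over-reject if there is correlation specific to those groups. At an assumed ICC of 0.05 a nominal 5% ANOVA is really about a 22% test with nothing shared across arms and 13% with half shared. It is near 5% only if the ICC is close to zero or the correlation is almost all shared. Three-arm Fisher is inflated in much the same way; pairwise Fisher less so.

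The direction follows from the design. The size rests on the assumed ICCs, equal groups of 20 and no dropout. Importance is moderate, because the tests are one exploratory strand in an unpowered pilot. For Aim 3 the protocol names no model, so the point there is only that no allowance for group is stated.

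**What to change.** In the Phase 2 analysis plan:

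1. Replace the Aim 2 tests with descriptive results by arm and by group: one summary per woman (such as the share of sessions attended), then the two group values shown for each arm. Do not use p-values to choose the component. This agrees with the Sample Size section.
2. If tests are kept, label them exploratory and analyse group means or group proportions with denominator df fixed by the design: 3, or 2 if blocked on start date. If Phase 1 changes the number of groups, reset the df to match.
3. For Aim 3, report effect sizes with the two group values for each intervention arm, and state that intervals ignoring group may be too narrow.

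This changes wording only and needs no extra women, groups or data. The cost is precision. The 95% half-width for a difference between two arms is 1.98 x sqrt(2/40) = 0.44 SD if group is ignored. At group level it is t x sqrt(ICC + (1 - ICC)/20), with nothing shared:

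| ICC | 3 df (t = 3.182) | 2 df (t = 4.303) |
|---|---|---|
| 0.01 | 0.78 SD | 1.05 SD |
| 0.05 | 0.99 SD | 1.34 SD |
| 0.10 | 1.21 SD | 1.64 SD |

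If one arm differs by 0.8 SD at ICC 0.05, the group-level test has 34% power with 3 df and 24% with 2 df. That is why descriptive reporting is the first choice.
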